1.2 Study Design

This is a Phase II single-arm, open-label, clinical study of the combination of LY3023414 (200 mg orally BID) and necitumumab (800 mg administered IV on Day 1 and 8 of each 21-day cycle) in patients with previously treated advanced or metastatic squamous non-small cell carcinoma of the lung.

Since the combination of LY3023414 and necitumumab will be given for the first time to humans, a safety lead-in will be conducted. After at least 6 patients (lead-in cohort) have been treated for a full cycle, a Safety Internal Monitoring Committee (SIMC) will conduct a review of the safety and available PK data to evaluate the

safety and PKs of the combination. If 2 (or more) of 6 patients in the lead-in cohort experience dose-limiting toxicities (DLTs) as defined in Section 5, 3 to 6 additional patients will be treated at a lower dose of study drug(s) following discussion of the safety data by the SIMC and assessed for DLTs. If there is a safety concern or PK interaction deemed to be clinically significant by the SIMC, the SIMC may recommend enrollment of approximately 6 additional patients to further evaluate the safety of the combination, or explore other doses of LY3023414 in combination with necitumumab. In the case of unacceptable and/or unmanageable toxicity of the combination at the intended dose level, the SIMC may decide to discontinue or modify the study (e.g. proceed with a lower dose level of study drug(s) tolerated in combination).

The total number of evaluable patients needed from the lead-in and the post lead-in cohort is approximately 48, with a planned interim analysis after 24 patients have completed up to 6 months of follow-up. An interim analysis will be performed purely for the purpose of detecting any early efficacy signal, and not for the purpose of stopping recruitment.

Cycles will be 21 days in length. Patients will be treated until disease progression as defined by Response Evaluation Criteria in Solid Tumors (RECIST) v 1.1, or they develop an unacceptable toxicity requiring discontinuation of the drug, or patient/physician choice. Patients will be evaluated for response to treatment after every 2 cycles.

The evaluable patients to assess the 6-months PFS event free rate are the FAS population defined in section 2.2.

The evaluable patients to assess the DLT rate are those patients who had been stay on study medication for more than 21 days, or have discontinued treatment due to DLT(s).

1.3 **Statistical Considerations**

SCRI DEVELOPMENT

INNOVATIONS

Sample Size Justification

CCI Based upon a 1-sided type I error rate of 20% and power of 90% the total sample size required to test the null hypothesis is 48 evaluable patients. A planned interim analysis will take place when 24 patients are evaluable for the primary endpoint, including the initial 6 patients treated at that dose to establish the safety and pharmacokinetics of the combination. The O'Brien Fleming alpha spending function is 0.067 at the interim analysis and 0.131 at the final analysis.

The sample size is calculated using EAST.

1.4 **Timing Of Analysis**

A Safety Internal Monitoring Committee (SIMC) will conduct a review of the safety and PK data after at least 6 patients (lead-in cohort) have been treated for a full cycle.

Interim efficacy analysis will take place when the first enrolled 24 treated, post leadin patients have finished tumor assessment at month 6 or early terminated from the trial for any reason. In addition to the efficacy analysis, the interim analysis will also include disposition, demographics, baseline characteristics, safety summary, and study drug administration.

The final analysis will take place when all of the 48 patients have finished tumor assessment at month 6 or early terminated from the trial for any reason.

1.5 **Responsibilities**

The final statistical analysis for the study will be performed by SCRI Development Innovations. Pharmacokinetic parameter estimation and modelling will be performed by Eli Lilly and Company.

1.6 Analysis Software

Analyses will be performed using SAS[®] version 9.3 or higher. PK parameter will be estimated WinNonlin[®] within Phoenix 6.3 or higher (Pharsight.a Certara [™] Company) and any software, approved and validated by Eli Lilly global PKPD organisation, to analyse the PK data using non-linear mixed effect modelling technics. A separate PK analysis plan is developed by Eli Lilly for the PK analysis.

2 Definition of Analysis Sets

In accordance with International Conference on Harmonization (ICH) recommendations in guidelines E3 and E9, the following analysis sets will be used for the analyses.

Detailed criteria for analysis sets will be laid out in Classification Specifications (CS) and the allocation of subjects to analysis sets will be determined prior to database hard lock.

2.1 All Patients

All patients who have signed the informed consent form (i.e. screening failures plus patients enrolled) will comprise the All Patients Set (ALL). The All Patients Set will be used to describe the patient disposition and all-cause deaths.

2.2 Full Analysis Set (FAS)

All enrolled patients who have received at least one dose of study medication will comprise the Full Analysis Set (FAS). This population will be used for the safety analysis and the primary analyses of the efficacy endpoints.

2.3 Per Protocol Analysis Set (PPAS)

All treated patients having no major protocol deviations will comprise the Per Protocol Analysis Set (PPAS). Those protocol deviations deemed to have an important impact on the analysis of study endpoints and leading to the exclusion of a patient will be listed in the Statistical Analysis Plan (SAP) prior to database lock. This analysis set will be used for sensitivity analyses of efficacy endpoints. The following are defined major protocol violations:

- Administration of prohibited concomitant medication as described in the Study Protocol.
- Violation of inclusion or exclusion criteria which may affect the assessment of the safety and/or efficacy of the study drug.

Prior to database lock, there will be a review of all reported protocol violations to determine the inclusion/exclusion of patients in each analysis set.

2.4 Safety Analysis Set (SAF)

All patients who have received at least one (full or partial) dose of study treatment will comprise the Safety Analysis Set (SAF). In this study, the Safety Analysis Set is same as the Full Analysis Set.

2.5 Pharmacokinetics Analysis Set (PKAS)

Pharmacokinetics Analysis Set (PKAS) includes patients who received LY3023414 200 mg orally twice daily (BID) and for whom the pharmacokineticist determines that there is sufficient data. The PKAS is used for all listings, tables and graphical summaries of the PK data.

2.6 Pharmacodynamic Analysis Set (PDAS)

Not Applicable.

2.7 Biomarker Analysis Set (BMAS)

Not Applicable.

3 Efficacy Parameters / Endpoints

3.1 Efficacy Endpoints

3.1.1 **Primary Efficacy Endpoint**

The primary efficacy endpoint is the 6-month DCR, which is defined as the number of patients with PFS > 6 months (or 26 weeks (182 days), to accommodate the scheduled tumor assessment at week 24 be delayed by up to 2 weeks) divided by number of patients in FAS population.

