3.1.3 Exploratory Efficacy Endpoints

Exploratory analyses including, but not limited to, according to biomarker status of EGFR and PI3K/mTOR signalling alterations may be performed as deemed appropriate.

3.1.4 **Other Efficacy Endpoints**

Not Applicable

3.2 **Definition of Endpoints**

3.2.1 6-Month Disease Control Rate

Disease Progression Date:

The disease progression date for the primary endpoint will be derived from the time point overall assessment based on radiological tumor assessment.

Progression Free Survival based on Tumor Assessment

Progression-free survival (PFS) is defined as the time from first dose until the date of radiological tumor assessment based disease progression (PD) or death. PFS will be censored in the following senarios:

- If patient has neither PD nor death, the PFS will be censored at last radiological tumor assessment date.
- Patients who have started on any subsequent anti-cancer therapy without any documentation of progression will be censored on the date of previous radiological tumor assessment date.
- If patient had PD or Death occurred more than 85 days (2 tumor assessment intervals) after previous tumor radiological assessment, the PFS will be censored at last radiological tumor assessment date.
- If patient does not have post baseline tumor assessment nor death within 85 days after first dose date, the PFS will be censored at Day 1.
- If patient does not have valid baseline tumor assessment, the PFS will be censored at Day 1.

Progression Free Survival Sensitivity Analysis Endpoints

To evaluate the robustness of the 6-month DCR based on the radiological tumor assessment, the PFS defined by both radiological progression and clinical progression will be analyzed as sensitivity analysis for the primary endpoints.

Therefore, the PFS2 will be defined as the time from first dose until the date of tumor assessment based disease progression (PD), clinical disease progression or death. The date of clinical disease progression is the last dose date of study medication when the patient has the end of treatment checked with "due to progressive disease".

Except the event is defined differently from PFS, the same censoring of the PFS will be applied when deriving PFS2.

The 6-month DCR is defined as the number of patients with PFS > 6 months (182 days) divided by number of patients in FSA population. Similarly, the 6-month DCR2 will be defined based on PFS2.

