3.3 General Rules in Deriving Time To Event Variables

The general rule for time to event analysis is described below:

Time To Event = Date of event with interest (with event) – Start Date + 1 day, if there is an event.

Time To Event = Last Date of event with interest (no event) – Start Date + 1 day, if there is no event.

If dates of event of interests are not available, the date of first dose will be used as event date (ie censored on day 1).

Start Date

Date of first dose is the start date to calculate the event.

Event Dates

For Overall Survival (OS), Progression-Free Survival (PFS) and Time To Progression (TTP), multiple dates will be used to derive the event dates for these endpoints, with the following rules:

- Events always take precedence to Censoring
- If multiple event dates are applicable, the earliest date will be used.
- If multiple censoring dates are applicable, the last date available will be used.

Cut-off Date

Any Event of interest after cut-off date will not be considered in the primary analyses. If the first event of interest is after cut-off date, the time to event variable will be censored to the previous date associated with the event of interest date. Follow-up evaluations of time to event measures may be conducted at a later date and appended to the CSR as appropriate.

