5.4 Efficacy Analysis

5.4.1 Analysis of Primary Variable

The primary endpoint, 6-month DCR, defined as the number of patients with PFS > 6 months (182 days) divided by number of patients in FAS population. The number will be presented as the point estimate with its associated 95% 80% two sided Clopper-Pearson confidence interval (CI).

Similiarly, the 6-month DCR defined based on PFS2 will be analyzed in the same manner.

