5.4.2 Analysis of Secondary Efficacy Variables

The ORR and DCR defined based on best overall response will be summarized along with the 80% Clopper Pearson CI.

Kaplan-Meier curves will be generated and the median time to event and the associated 95% CI will be provided for PFS, PFS2(based on clinical progression) and OS. Survival rates at 3 months, 6 months, 9 months and 12 months will also be provided based on Kaplan-Meier curves for PFS, PFS2 and OS.

Categorical summary of change in ECOG will be summarized.

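### A clean, on-time week-24 scan counts as a primary-endpoint failure unless a scan or event after Day 182 is on file, and no stated data cut-off guarantees one

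*SAP*

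**What the plan says.** **Endpoint.** SAP 3.1.1 requires "PFS > 6 months (or 26 weeks (182 days), to accommodate the scheduled tumor assessment at week 24" running late. SAP 5.4.1 repeats it: "defined as the number of patients with PFS > 6 months (182 days) divided by number of patients in FAS population". Protocol 10.4.2.1 uses the same 26-week threshold.

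**Censoring.** SAP 3.2.1: "If patient has neither PD nor death, the PFS will be censored at last radiological tumor assessment date". It also sends late events back to the last scan: "If patient had PD or Death occurred more than 85 days (2 tumor assessment intervals) after previous tumor radiological assessment". Patients who start new anticancer therapy without documented progression are censored at the preceding scan. Under SAP 3.3 a censored time is the last relevant date minus "Start Date + 1 day, if there is no event", with first dose as the start. SAP 3.4 allows no imputation.

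**Scans.** Cycles last 21 days and tumours are imaged every two cycles (protocol 7.4 and Appendix E; SAP 1.2 and 3.2.2). Protocol 10.4.2 says every three cycles.

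**Timing.** SAP 1.4: "The final analysis will take place when all of the 48 patients have finished tumor assessment at month 6" or have terminated early. Protocol 10.5.1 has the same trigger but is also met by stopping study drug. Protocol 10.5.2 ties the interim to the month-6 scan of 24 patients. SAP 3.3 adds: "Any Event of interest after cut-off date will not be considered in the primary analyses". No date or minimum follow-up is given for that cut-off.

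**Decision rule.** Protocol 10.5.2 sets efficacy boundaries of 44% (interim) and 36% (final) on the 6-month DCR. As a secondary analysis, SAP 5.4.2 says: "Survival rates at 3 months, 6 months, 9 months and 12 months will also be provided based on Kaplan-Meier curves".

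**The concern.** Each rule is ordinary alone; the trouble is the combination. The 182-day threshold lies beyond the week-24 visit, censoring stops the clock at the last scan, and the analysis is triggered by the week-24 visit itself. A patient whose month-6 scan is on time and clean has a censored time short of the threshold, and the proportion treats a censored time of 169 days exactly like a failure.

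The patient becomes a success only if something later is in the data. A scan showing progression at week 30 would do it. So a patient known to have progressed at week 30 is counted as controlled, while one who is alive, progression-free and not yet rescanned is not.

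How many patients this affects depends on a cut date that the plan does not set, in an open-label trial. The observed DCR and the chance of passing the 36% boundary both move with that date.

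**Working it through.** **1. The plan's own figures.** 26 × 7 = 182 days. Two 42-day intervals plus one day is 2 × 42 + 1 = 85, the SAP's missed-scan limit. Both figures fit the 2-cycle schedule.

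**2. Scan days under the SAP 3.3 day count.** Day = 42k + 1, giving Days 43, 85, 127, 169 and 211. Week 24 is Day 169, and 169 > 182 is false. A scan d days late falls on Day 169 + d, which exceeds 182 only when d ≥ 14. Delays of 0, 7, 13 and 14 days give 169, 176, 182 and 183. So a clean scan up to 13 days late fails and one exactly 14 days late passes. By the same one-day slip, progression found at a scan exactly two weeks late (Day 183) counts as a success.

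**3. What turns a clean week-24 patient into a success.**
- A week-24 scan 14 or more days late.
- Any later scan after Day 182, clean or not. Progression at Day 211 is 42 days after Day 169, inside the 85-day limit, so PFS = 211.
- A death from Day 183 to Day 169 + 85 = 254.

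A patient who starts new therapy after a clean Day-169 scan and before any later scan stays at 169 whatever the cut.

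**4. How many patients have no week-30 scan.** Assume 48 patients enter uniformly over 365.25 days (12 months' enrolment is planned; uniformity is assumed), scans are on time, and the cut is L days after the last patient's week-24 scan. For L < 42 the last patient is always affected, and the expected total is 1 + 48 × (42 − L)/365.25:
- L = 0: 1 + 5.52 = 6.5
- L = 14: 1 + 3.68 = 4.7
- L = 28: 1 + 1.84 = 2.8
- L = 42: 0

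At a 45% true rate this loses 2.9, 2.1, 1.3 and 0 successes.

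**5. Rates and rules.** The hypotheses are redacted, so rates are back-solved. For the interim boundary, 0.30 + z(1 − 0.067) × √(0.3 × 0.7/24) = 0.44, and the 36% final boundary also returns 0.30. With 45% as the alternative, a two-look normal approximation gives alpha 0.2005 and power 0.902, close to the stated 20% and 90%. The final rule is ≥ 18/48 (17/48 = 35.4%, 18/48 = 37.5%) and the interim rule ≥ 11/24 (10/24 = 41.7%, 11/24 = 45.8%).

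**6. Chance of meeting the boundary.** The no-loss column is exact binomial. The others come from simulation (200,000 trials per cell) in which a controlled patient is lost if week 30 falls after the cut. Progression and death between week 24 and the cut are not modelled.

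| Look, true rate | No loss | Cut +0 wk | +2 wk | +4 wk | +6 wk |
|---|---|---|---|---|---|
| Final, 30% | 0.16 | 0.05 | 0.08 | 0.11 | 0.16 |
| Final, 40% | 0.69 | 0.38 | 0.47 | 0.56 | 0.69 |
| Final, 45% | 0.88 | 0.63 | 0.72 | 0.80 | 0.88 |
| Final, 50% | 0.97 | 0.83 | 0.89 | 0.93 | 0.97 |
| Interim, 45% | 0.55 | 0.13 | 0.22 | 0.34 | 0.55 |

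Exact cross-check: with k patients forced to failure, P(Bin(48 − k, 0.45) ≥ 18) is 0.858, 0.794 and 0.666 for k = 1, 3 and 6, and the expected DCR falls from 45% to 44.1%, 42.2% and 39.4%. At zero lag and 45%, accrual over 9, 12 or 18 months gives 0.53, 0.63 or 0.72.

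**7. The other scan schedule.** Every three cycles gives Days 64, 127 and 190. Since 190 > 182, the problem largely disappears, but that schedule has no week-24 scan, which the endpoint definition names.

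**The case against.** The best case for the plan is that only a cut-off rule is missing and the endpoint is sound. The 182-day threshold makes progression found at a late week-24 scan count as failure, and with mature data the Day-211 scan settles every patient on schedule. A patient who progresses at week 30 really was progression-free at 6 months, so counting that patient as a success is right. That is fair: the fault is failing the clean, not-yet-rescanned patient.

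The triggers say when analysis happens, not that data freeze that day. Queries and analysis-set review come before database lock, and scanning continues meanwhile. So zero lag is a bound, not a forecast. A cut-off might also be set in documents not available here (the classification specifications, the DMC charter, or SAP Appendix 4, present by title only). None of this guarantees a scan after Day 182.

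On-time scanning inflates the loss. If 30% of patients had accumulated 14 or more days' delay (an assumption), zero-lag power at 45% would be 0.72, not 0.63, and at four weeks 0.83, not 0.80. The loss shrinks but remains.

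The bias is conservative, the interim does not stop recruitment, and the Kaplan-Meier 6-month rate would expose a discrepancy. All true, but that rate is secondary and the boundaries apply to the simple proportion. SAP 1.2 does speak of a 6-month event-free rate, which could be read as treating censored patients differently. Two readings of the primary endpoint are themselves a reason to amend.

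Finally, scoring the week-24 scan within a window accepts scans before Day 169 and so loosens the endpoint somewhat. This stands, and is why an alternative that leaves the endpoint unchanged is offered below.

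**Conclusion.** The concern holds. Followed as written, the SAP gives a PFS of 169 days to a patient with a clean on-time week-24 scan and nothing later, and scores that patient a failure. Nothing in either document ensures a scan after Day 182 for patients enrolled in roughly the last six weeks, or for the latest of the first 24 at the interim.

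The mechanism follows from the SAP's own rules on the 2-cycle schedule. Starting PFS at enrolment, as in protocol 10.4.2.2, would help only if first dose came at least 14 days later.

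The size is conditional. With uniform 12-month accrual, on-time scans and a 45% true rate, the final-look chance of success is 0.63 to 0.88 for cuts 0 to 6 weeks after the last week-24 scan, against 0.88 intended. At 30%, the chance of wrongly passing falls too, from 0.16 to 0.05 at zero lag. The direction is downward: a promising combination could be missed, but a false claim is not made more likely. Because this is the sole primary endpoint and the result depends on an unstated date, it should be corrected before any analysis.

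**What to change.** **Score week-24 status directly** (SAP 3.1.1, 3.2.1, 5.4.1; protocol 10.4.2.1). Count a patient as controlled if all three hold:
1. No progression or death up to the end of week 26.
2. No subsequent anticancer therapy before the qualifying scan.
3. A progression-free scan within a stated window around Day 169 (for example 14 days either side) or later.

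All other FAS patients are failures. State whether week 26 ends on Day 182 or Day 183, since a scan exactly 14 days late is Day 183. In SAP 1.4 and 3.3 and protocol 10.5.1 and 10.5.2, set the cut when every patient has passed that day with the week-24 scan done, or has progressed, died, been lost to follow-up or left the study. Stopping study drug alone should not qualify.

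**Alternative that leaves the endpoint unchanged.** Keep the 182-day threshold and hold the cut until every progression-free patient still in follow-up has a scan after Day 182 (week 30 for those on treatment). Patients who start new therapy after a clean on-time week-24 scan and before any later scan would still be failures; the SAP should say whether that is intended.

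Either way, reconcile the 3-cycle scan text in protocol 10.4.2 with the 2-cycle schedule elsewhere.

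**Cost.** A short SAP amendment and a protocol amendment to the sections named, with no extra patients or procedures. The cut moves about two weeks later under the first option and about six under the alternative. It moves later still under the alternative for patients off drug before progression, who are seen only every 3 months ± 1 month (protocol 7.6.1).

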3.1.2 Secondary Efficacy Endpoints

- Overall Response Rate (ORR)
- Disease Control Rate Based on Best Overall Response
- Progression–free survival (PFS)
- Overall survival (OS)

3.1.3 Exploratory Efficacy Endpoints

Exploratory analyses including, but not limited to, according to biomarker status of EGFR and PI3K/mTOR signalling alterations may be performed as deemed appropriate.

3.1.4 **Other Efficacy Endpoints**

Not Applicable

3.2 **Definition of Endpoints**

3.2.1 6-Month Disease Control Rate

Disease Progression Date:

The disease progression date for the primary endpoint will be derived from the time point overall assessment based on radiological tumor assessment.

Progression Free Survival based on Tumor Assessment

Progression-free survival (PFS) is defined as the time from first dose until the date of radiological tumor assessment based disease progression (PD) or death. PFS will be censored in the following senarios:

- If patient has neither PD nor death, the PFS will be censored at last radiological tumor assessment date.
- Patients who have started on any subsequent anti-cancer therapy without any documentation of progression will be censored on the date of previous radiological tumor assessment date.
- If patient had PD or Death occurred more than 85 days (2 tumor assessment intervals) after previous tumor radiological assessment, the PFS will be censored at last radiological tumor assessment date.
- If patient does not have post baseline tumor assessment nor death within 85 days after first dose date, the PFS will be censored at Day 1.
- If patient does not have valid baseline tumor assessment, the PFS will be censored at Day 1.

Progression Free Survival Sensitivity Analysis Endpoints

To evaluate the robustness of the 6-month DCR based on the radiological tumor assessment, the PFS defined by both radiological progression and clinical progression will be analyzed as sensitivity analysis for the primary endpoints.

Therefore, the PFS2 will be defined as the time from first dose until the date of tumor assessment based disease progression (PD), clinical disease progression or death. The date of clinical disease progression is the last dose date of study medication when the patient has the end of treatment checked with "due to progressive disease".

Except the event is defined differently from PFS, the same censoring of the PFS will be applied when deriving PFS2.

The 6-month DCR is defined as the number of patients with PFS > 6 months (182 days) divided by number of patients in FSA population. Similarly, the 6-month DCR2 will be defined based on PFS2.

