10.5.2 Planned Interim Analysis

Interim analysis will be conducted when a total of 24 patients have had month 6 tumor assessment. A 6-month DCR rate of 44% will be used as the boundary to access the efficacy during the interim analysis. A 6-month DCR rate of 36% will be used as the boundary to assess the efficacy of LY3023414 and necitumumab in the final analysis.

The results from the interim analyses will be examined by a committee that will be established prior to the inclusion of the first patient in the trial. The committee will consist of at least a Lilly medical director, a Lilly clinical research physician/clinical research scientist, and a Lilly statistician and will make recommendations about the trial. The outcome of the interim analyses will be documented, and a written letter will be submitted to the IRB(s) and the investigators for documentation purposes. Enrollment will continue while the interim analysis is being performed.

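### The SAP's 85-day PFS gap rule fits only the on-treatment scan schedule and is not ranked against SAP 3.3, so the 6-month DCR can be derived in two ways

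*SAP*

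**What the plan says.** SAP 3.2.1 lists the situations in which PFS is censored. One is a late event: "If patient had PD or Death occurred more than 85 days (2 tumor assessment intervals) after previous tumor radiological assessment". The consequence follows: "after previous tumor radiological assessment, the PFS will be censored at last radiological tumor assessment date". Another bullet censors patients who start new anticancer therapy without documented progression.

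SAP 3.3, which names PFS, states "Events always take precedence to Censoring" and "If multiple censoring dates are applicable, the last date available will be used". It adds "Any Event of interest after cut-off date will not be considered in the primary analyses".

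The 6-month DCR is the number of FAS patients with PFS above 182 days, divided by the FAS (SAP 3.1.1, 3.2.1 and 5.4.1). Protocol 10.5.2 sets the final criterion: "A 6-month DCR rate of 36% will be used as the boundary to assess the efficacy".

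On treatment, scans come every 2 cycles of 21 days (Protocol 7.4, Appendix E), although Protocol 10.4.2 says every 3 cycles. Patients who stop before progression are followed every 3 months ± 1 month from last dose (Protocol 7.6.1), with CT marked for those visits in Appendix E. The end-of-treatment CT may be skipped if a scan was done within the previous 8 weeks (Protocol 7.5). Protocol 10.4.2.2 has no gap rule but leaves detailed PFS derivation to the SAP.

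**The concern.** A gap rule is meant for patients whose assessments were missed, so that the time of progression is poorly known. Here the limit is shorter than one nominal off-treatment interval, so it can also remove an event found exactly on schedule. SAP 3.3, read literally, gives the opposite instruction for the same event, and no text ranks the two sections.

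This reaches the primary endpoint. A patient censored on or before Day 182 stays in the denominator and counts as a failure. The same patient counts as controlled if the event is dated after Day 182.

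No planned analysis would show the difference. The sensitivity endpoint keeps the rule ("Except the event is defined differently from PFS, the same censoring of the PFS will be applied when deriving PFS2"), and the per-protocol analysis changes only the population. SAP 5.4.2 also plans that "Survival rates at 3 months, 6 months, 9 months and 12 months will also be provided based on Kaplan-Meier curves". The gap rule lowers the DCR but tends to raise the Kaplan-Meier rate, so the two 6-month figures can drift apart.

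A smaller wording fault lies in the rule itself. The gap runs from the previous scan, but censoring is at the last scan, which for a progression could be taken to mean the progression scan.

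**Working it through.** **1. The plan's own figure.** 2 intervals x 2 cycles x 21 days = 84; 84 + 1 = 85. The figure reproduces for on-treatment scans. With the every-3-cycles text of Protocol 10.4.2, two intervals would be 2 x 63 = 126 days.

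**2. Off treatment.** 3 x 30.44 = 91 days nominal; 2 to 4 months is about 61 to 122 days. So 85 days is 85/91 = 0.93 of one nominal interval, and two nominal intervals are about 183 days.

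**3. Effect of the CT waiver on the first gap.** Let u be the days from last scan to last dose, assumed uniform on 0–42. With an end-of-treatment visit 30 days after last dose, a CT is needed only if u + 30 > 56, that is u > 26.
- u > 26: nominal gap 91 − 30 = 61 days, under the limit.
- u ≤ 26: nominal gap 91 + u ≥ 91 days, over the limit.

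The chance of exceeding 85 days is 26/42 = 62% at nominal visits, and about 55% with the ± 1 month window. If a treatment visit doubles as the end-of-treatment visit (Protocol 7.5 allows this), u never reaches 56, the CT is always waived, and the figures are 100% and 89%.

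**4. A patient on schedule.** Scan and last dose on Day 126 without progression; end-of-treatment visit on Day 156 with CT waived (30 days since the scan); follow-up scan on Day 126 + 91 = 217 shows progression. The gap is 91 days.
- Event counted on its date (3.3): PFS 217, event, controlled at 6 months.
- Gap rule (3.2.1): PFS censored at 126, not controlled.

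**5. Who can change status.** Only a patient with the previous scan on or before Day 182, an event after Day 182 but before the cut-off, a gap over 85 days, and no new therapy. Early stoppers are the main such group among patients followed on schedule.

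**6. Boundary.** 0.36 x 48 = 17.28. Since 17/48 = 35.4% and 18/48 = 37.5%, one patient can decide it.

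**7. Size, by simulation.** Assumptions: exponential PFS with 30% or 45% progression-free at Day 182; 20% of events are deaths, dated exactly; progression is found at the next scan; on-treatment scans every 42 days; 20% stop before their event (uniformly in time or at constant hazard); nominal or windowed follow-up visits. New-therapy censoring is kept in both derivations.

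| Setting | Event-date DCR | Gap-rule DCR | Patients of 48 | Opposite sides of 36% |
|---|---|---|---|---|
| No new therapy, no cut-off, true 30% | 33.8–33.9% | 30.4–31.3% | 1.0–1.7 (both true rates) | 12–17% |
| Same, true 45% | 48.1–48.5% | 45.7–46.1% | as above | 3–5% |
| Half start new therapy, cut-off at last patient's Day 182 | lower | lower | about 0.6 | roughly 2–7% |

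Without new therapy or cut-off, the patient count is 0.5–0.8 at 10% stopping and 1.7–2.7 at 30%.

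Kaplan-Meier, first setting, uniform stopping, nominal visits: the gap rule gives a DCR of 31.0% beside a 6-month PFS of 35.7%; the event-date derivation gives 33.8% for both.

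**8. Check with no early stopping.** The DCR is already about 32% (true 30%) and 47% (true 45%), because scans on Days 168 and 210 straddle Day 182.

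**The case against.** The best defence is that 3.3 is headed as general rules while 3.2.1 lists named scenarios for this endpoint. A literal 3.3 would delete not only the gap rule but also the new-therapy rule, whenever an event follows the new therapy. Few programmers would do that, so 3.2.1 as the specific exception is the more natural reading. This stands, but the SAP does not say so, and 3.3 uses the word always.

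A reader might infer that a third derivation, censoring at the progression scan itself, is seriously open. For a death, previous and last scan are the same, so the intended meaning is almost certainly the last scan before the event. This is a wording slip.

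A reader might also infer that 85 days always falls short of an off-treatment interval. It does so only at the nominal 3 months. Early visits, or an end-of-treatment CT that is actually done, can bring the gap under the limit.

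The effect shrinks with new therapy and with a cut-off, because the final analysis does not wait for the follow-up scans of early stoppers (Protocol 10.5.1, SAP 1.4). Treatment until progression, with single-agent continuation allowed, also limits the group. These points stand and set the lower end of the range.

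Finally, the SAP must be approved before database lock (Protocol 10.4), and its appendix of derived-variable specifications is not visible. The documents therefore do not show that the choice would be made after results are seen.

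**Conclusion.** The point holds as an ambiguity in the primary endpoint's derivation and a limit that does not match the off-treatment schedule. It should be corrected, but the expected effect is small. At an assumed 20% stopping early, about 0.6 of 48 patients (half start new therapy, cut-off at the last patient's Day 182) to about 1.7 (neither) change status. The two derivations then disagree about the 36% boundary in roughly 2–17% of trials. The stopping share, the PFS shape and the share starting new therapy are all assumptions.

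Two stronger conclusions are not supported. Having a gap rule is not itself an error, since the protocol leaves derivation to the SAP. Nor can it be said which derivation is nearer the truth. Much of the excess over the true rate comes from ordinary 42-day scanning, and the rest depends on new therapy and the cut-off. In the worked patient nothing was observed at Day 182: if progression is equally likely anywhere in the gap, the chance that it came by then is (182 − 126)/(217 − 126) = 62%.

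**What to change.** Amend the SAP before database lock:

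1. State whether the censoring scenarios in 3.2.1 (gap rule and new therapy) are exceptions to 3.3.
2. Refer to the last radiological assessment before the event in both halves of the gap rule.
3. Make the limit and its two-interval label match the scan schedule in force, on and off treatment, and reconcile the every-3-cycles text of Protocol 10.4.2 with the every-2-cycles schedule.
4. Name the 6-month DCR that is compared with 36%. Add one sensitivity analysis of PFS and 6-month DCR that counts every documented progression or death before new anticancer therapy on its date. Note that, relative to the gap rule, it can only raise the DCR, because the event always falls after the previous scan.

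The cost is SAP wording, derivation code and one extra analysis, plus a correction to the protocol text in item 3; no visit or scan changes. The drawback is that two DCRs are reported and may fall on opposite sides of the boundary, which is why the primary one must be named in advance.
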